14. STUDY MEDICATION EXPOSURE

Exposure to study medication will be presented for the SAF Set. Investigational product administration for each subject will be summarized in terms of the total number of patches applied by visit, number of patches removed early (due to safety reasons: irritation, discomfort, etc.) by visit, and summary of the reason for early removal.

Each subject’s duration of exposure (days) will also be calculated and summarized by treatment arm.

Derivation:

Duration of exposure (days) = latest of (last patch application date and last patch removal date)
- date of 1st patch application + 1

Refer to [Appendix 4](#) for more details.

A by-subject listing of all drug exposure information collected will be presented.

Noven Pharmaceuticals, Inc.

Protocol HP-5000-US-07

Statistical Analysis Plan

Page 26 of 58

The daily amount of rescue medication used and the daily amount of study drug used will be calculated and presented in a by-subject listing. Deviations from the planned doses (overdose, missed dose, or timing) will be recorded on the eCRF and presented in by-subject listing.

15. STUDY MEDICATION TREATMENT COMPLIANCE

Treatment compliance with study drug regimens will be presented via the counting of returned unused patches, patch application, removal, and by questioning the subject, at every post-randomization visit. Treatment compliance will be calculated as number of patches given less the number of patches returned divided by the number of days for required applications, expressed as a percentage. The total number of days between study visit dates will be used for the calculation to determine the number of days for required applications. Unscheduled patch applications will be considered in the calculation.

Number and percentage of subjects who are compliant (defined as using $\geq 80\%$ and $\leq 120\%$ of study medication), noncompliant (defined as using less than 80% or more than 120% of study medication) at each treatment arm will be presented by visit and overall. A summary table will also present overall subject compliance with study drug. A by-subject listing of all drug exposure information collected will be presented.

16. EFFICACY OUTCOMES

16.1 PRIMARY EFFICACY

16.1.1 PRIMARY EFFICACY VARIABLE AND DERIVATION

The primary efficacy variable is the change from baseline to Week 12 in the WOMAC pain score.

This score, is derived by summing the sub-scores for the 5 following items collected in the *Western Ontario and McMaster Universities Osteoarthritis Index* eCRF page taking into account missing observations as described in [section 7.3](#):

Question: How much pain have you had:

Noven Pharmaceuticals, Inc.

Protocol HP-5000-US-07

Statistical Analysis Plan

Page 27 of 58

Each item is rated from 0 to 4, with 0 being none and 4 being extreme.

Therefore, the WOMAC pain score will either have an integer value from 0 to 20 or a missing value for each visit.

16.1.2 MISSING DATA METHODS FOR PRIMARY EFFICACY VARIABLE

The primary analysis method for evaluating the primary efficacy endpoint is the likelihood-based analysis of repeated measures, a mixed model with repeated measures (MMRM) under an assumption that the missing observations of change from baseline WOMAC pain score are missing at random. To assess the robustness of the MAR assumption, sensitivity analyses which utilize multiple imputations and different assumption about unobserved outcomes will be performed, as detailed in [Section 16.1.4](#).

16.1.3 PRIMARY ANALYSIS OF PRIMARY EFFICACY VARIABLE

The estimand in the primary analysis for efficacy is the difference between treatment groups (HP-5000 *and* placebo) in the change from baseline to Week 12 in WOMAC pain score. The analysis will be performed using the ITT analysis set taking into account intercurrent events using the composite strategy. [\[4.5\]](#) The study treatment discontinuation due to reasons related to study treatment (e.g. AE, LOE, etc.), rescue medication use within 24 hours of WOMAC pain assessment, removal/detachment of the patch for more than 24 hours before WOMAC pain assessment are defined as intercurrent events. Only the reasons that are in the database will be presented in the table.

The treatment effect on the primary efficacy variable which is change from baseline to Week 12 in WOMAC pain score will be evaluated using an MMRM model for the ITT Set and as well as taking into account following intercurrent events, and composite strategy (see [section 16.1.4](#)).

The MMRM model will include change from baseline in WOMAC pain score as the repeated dependent variable, with effects for treatment (HP-5000 and placebo), visit, treatment-by-visit interaction, and the baseline WOMAC pain score as a covariate. Initially an unstructured covariance matrix will be assumed. If convergence is not achieved with this initial structure, additional variance-covariance structures will be tested and the one with the smallest AIC will be chosen. The Kenward-Roger method will be used to estimate the denominator degrees of freedom and correct for bias in the estimated variance-covariance of the fixed effects. This MMRM with the covariance structure that converges will be used to compare the HP-5000

Noven Pharmaceuticals, Inc.

Protocol HP-5000-US-07

treatment to placebo. The sample SAS code for any MMRM can be found in [Appendix 2](#).

For each visit, the least-squares mean (LSM) estimate, standard error, and 95% CIs will be presented for each treatment group. The least square mean difference of the treatment from placebo estimate, standard error, 95% CI, effect size, and p-value for each visit will also be presented in this table. The effect size is calculated as the difference in the LS mean estimate divided by the pooled estimate of within subject standard deviation obtained from the variance-covariance matrix used in the model. Descriptive statistics for the WOMAC pain score and change from baseline in WOMAC pain score will be presented in a table by visit and treatment group.

Additionally, if the normality assumption is not supported by the data, an analysis of covariance (ANCOVA) on rank-transformed data will be used as utility analysis and additional supportive analyses may be performed if necessary.

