The primary efficacy variable, change from Baseline to Week 12 in the WOMAC pain score, will be analyzed using a mixed model repeated measures (MMRM) analysis. The MMRM model will include change from Baseline in WOMAC pain score as the repeated dependent variable, with treatment (HP-5000 and placebo), visit, treatment-by-visit interaction, and the Baseline WOMAC pain score as covariates. An unstructured covariance matrix will be assumed. If the unstructured covariance matrix fails to converge, a series of other covariance structures will be tested for use.

Other sensitivity analyses will be performed on the primary endpoint to assess the robustness of the results based on the model used for primary analysis as described below.

The use of MMRM inherently implies that the treatment effect on the change from baseline in the WOMAC score will be similar for the patients who withdraw and for those who complete the study in their respective treatment groups, conditional on the outcomes observed prior to withdrawal (MAR [Missing at random] assumption). To assess the robustness of the MAR assumption, sensitivity analyses which utilize multiple imputations and a different assumption about unobserved outcomes will be performed, as detailed below.

A number of sensitivity analyses of the primary efficacy endpoint will be performed to assess the impact of assumptions about unobserved missing data patterns on the primary inferences after intercurrent events in the trial.

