2.2.1 OTHER SECONDARY EFFICACY OBJECTIVES

- To evaluate the effect of HP-5000 on pain among subjects with OA of the knee at Weeks 1, 2, 4, and 8
- To evaluate the effect of HP-5000 on physical function among subjects with OA of the knee at Weeks 1, 2, 4, and 8

 Noven Pharmaceuticals, Inc.

Protocol HP-5000-US-07

- To evaluate the effect of HP-5000 on stiffness among subjects with OA of the knee at Weeks 1, 2, 4, and 8
- To evaluate the effect of HP-5000 on pain intensity as measured by numeric rating scale (NRS) scores on a daily diary
- To evaluate the onset of effect of HP-5000 on pain among subjects with OA of the knee
- To evaluate the pattern of use of rescue medication in the study
- To evaluate skin irritation, discomfort, and adhesion following administration of HP-5000
- To evaluate the safety and tolerability of HP-5000
- To evaluate the effect of HP-5000 treatment on Quality of Life (QOL)

Other Secondary Efficacy Endpoints for these objectives are:

- WOMAC LK3.1 OA (pain) change from baseline at Weeks 1, 2, 4, and 8
- WOMAC LK3.1 OA (physical function) change from baseline at Weeks 1, 2, 4, and 8
- WOMAC LK3.1 OA (stiffness) change from baseline at Weeks 1, 2, 4, and 8
- WOMAC LK3.1 OA (composite score) change from baseline at Weeks 1, 2, 4, 8, and 12
- Change from baseline in pain intensity assessed on an 11-point NRS at Weeks 1, 2, 4, 8, and 12
- Change from baseline in pain intensity assessed on an 11-point NRS of a weekly average of all available daily pain scores at each week from Week 1 through 12
- Change from baseline in Patient Global Assessment (PGA) at Weeks 1, 2, 4, 8, and 12
- Patient Global Impression of Change (PGIC) at Weeks 1, 2, 4, 8, and 12
- Treatment Response: Reduction in the WOMAC LK3.1 OA Index (pain) of $\geq 30\%$, $\geq 50\%$, $\geq 70\%$, and $\geq 90\%$ at Weeks 1, 2, 4, 8, and 12
- Treatment Response: Reduction in the WOMAC LK3.1 OA Index (physical function) of $\geq 30\%$, $\geq 50\%$, $\geq 70\%$, and $\geq 90\%$ at Weeks 1, 2, 4, 8, and 12
- Treatment Response: Reduction in the WOMAC LK3.1 OA Index (stiffness) of $\geq 30\%$, $\geq 50\%$, $\geq 70\%$, and $\geq 90\%$ at Weeks 1, 2, 4, 8, and 12
- Rescue Medication Use during Treatment Phase: Proportion of subjects who used, number of days used, and total number of tablets

Noven Pharmaceuticals, Inc.

Protocol HP-5000-US-07

Statistical Analysis Plan

Page 13 of 58

- Onset of the effect: Change from baseline pain intensity assessed on an 11-point NRS

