Double-blind Treatment Phase: Subjects will apply a single patch to the target knee [REDACTED]

[REDACTED] After the removal of the patch [REDACTED], a new patch will be applied to a different site on the target knee. Subjects will be instructed to rotate the patch application site [REDACTED] to alternate sides (inner and outer) of the target knee. During the Double-blind Treatment Phase, subjects will also complete a daily eDiary to record patch application and removal time, adhesion, irritation, discomfort, and pain assessments; and

Noven Pharmaceuticals, Inc.

Protocol HP-5000-US-07

Statistical Analysis Plan

[figure not shown]
Page 15 of 58

amount of rescue medication (APAP) taken daily, if applicable. A maximum of 2 g/day of APAP will be allowed as rescue medication except from Baseline Visit until Visit 4, within 2 calendar days prior to all subsequent visits (V5, V6, V7, and V8), and on the day of the clinic visits (V4, V5, V6, V7, and V8).

NOTE: Subjects are NOT allowed to apply HP-5000 on the non-target knee at any time during the study.

Follow-up Phase: Subjects will have a safety visit approximately 7 days after the Week 12 End-of-Treatment Visit. The investigator or qualified study staff will contact all subjects by phone for continued safety monitoring of AEs. At the discretion of the investigator, subjects may have to return to the clinic for their Follow-up Visit.

Figure 1: A Schematic of the Study Design

Sample Size: Based on the HP-5000 Phase 2 study results, the assumed effect size of the test product in the pivotal study will be about [REDACTED]. The sample size of [REDACTED] subjects per treatment arm (or total of about [REDACTED] subjects) will be included in order to have 80% power to demonstrate statistically significant difference versus placebo using a 2-sided overall Type I Error rate of 0.05.

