16.2.2. ANALYSIS OF KEY SECONDARY EFFICACY VARIABLES

The MMRM models for the key secondary efficacy variables will include change from baseline in WOMAC physical function (or stiffness) score as the repeated dependent variable, with effects for treatment (HP-5000 and placebo), visit, treatment-by-visit interaction, and the baseline WOMAC physical function (or stiffness) score as a covariate. Initially an unstructured covariance matrix will be used to model the correlation among repeated measurements within subject.

If the unstructured covariance matrix fails to converge, the same procedure for selection of covariance structures as was specified for the primary efficacy will be done as listed in [section 16.1.3](#). Descriptive and inferential statistics, comparable to those described in [sections 16.1.3 through 16.1.6](#) for the primary efficacy variable will be presented for each of the key secondary efficacy variables.

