APPENDIX 2. SAS CODE

PROC MIXED:

```
ODS OUTPUT LSMEANS=LSEST DIFFS=LSDIFF COVPARMS=COVS;
PROC MIXED DATA = TEST COVTEST;
CLASS TREATMENT VISIT SUBJECT;
MODEL change in womac pain score = treatment visit treatment*visit baseline womac pain
score;
LSMEANS TRTPN*AVISITN / DIFF CL;
REPEATED VISIT / TYPE = UN SUBJECT = SUBJECT;
RUN;
```

PROC LOGISTIC:

```
proc logistic data="Test" descending;
where visit variable = a given number (e.g., 4)
class treatment / param=ref ;
model respond = treatment PGA baseline value;
run;
```

[REDACTED]

Noven Pharmaceuticals, Inc.

Protocol HP-5000-US-07

[REDACTED]

Statistical Analysis Plan

Page 56 of 58

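### The primary MMRM fits one baseline slope to all five visits; adding baseline-by-visit may recover a little Week 12 precision at almost no cost

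*SAP*

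**What the plan says.** The same model appears wherever the primary analysis is described.

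- SAP 16.1.3 lists treatment, visit, "treatment-by-visit interaction, and the baseline WOMAC pain score as a covariate".
- The PROC MIXED code in SAP Appendix 2 agrees: "MODEL change in womac pain score = treatment visit treatment*visit baseline womac pain".
- Protocol 13.4.3.1 and the synopsis give the same terms: "treatment-by-visit interaction, and the Baseline WOMAC pain score as covariates".
- For physical function and stiffness, SAP 16.2.2 repeats the form: "treatment-by-visit interaction, and the baseline WOMAC physical function (or stiffness) score as a covariate". Protocol 13.4.3.2 does too.

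WOMAC has five post-baseline visits, as the endpoint list shows: "WOMAC LK3.1 OA (composite score) change from baseline at Weeks 1, 2, 4, 8, and 12". For the covariance, "Initially an unstructured covariance matrix will be assumed".

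No planned analysis frees the baseline slope. The supplementary analysis in SAP 16.1.6 refits the model without adjusting for intercurrent events. The imputation analyses in Appendix 3 apply the primary MMRM to each completed dataset.

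**The concern.** The model lets the treatment effect and, through the unstructured matrix, the variances and correlations change freely from visit to visit. Baseline is the one element held constant. The outcome is change from baseline, so if the correlation between baseline and follow-up weakens over 12 weeks while the follow-up SD stays about the same, the slope becomes more negative at later visits. The common slope is a weighted average over visits. Week 12 is the last visit and the only primary time point, so under steady drift it lies furthest from that average on the late side.

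An unstructured covariance does not remove the misfit. It absorbs it into the Week 12 variance, which sets the standard error of the primary comparison. At stake is a small part of the precision of that comparison, in a trial planned at 80% power where function and stiffness are tested only if pain succeeds.

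**Working it through.** **The plan's own figure.** The SAP states "80% power to demonstrate statistically significant difference versus placebo using a 2-sided overall Type I Error rate of 0.05". The effect size and sample size are redacted, so this cannot be reproduced. For scale, 80% power needs n = 2(1.960 + 0.842)²/d² per arm: 393, 252, 175, 129 and 99 for d = 0.20, 0.25, 0.30, 0.35 and 0.40.

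**Inputs.** From the documents: five visits, unstructured covariance, two-sided alpha 0.05, 80% power, and an SD of the primary endpoint below 4 points (Appendix 3 calls 4 reasonably higher than 1 SD). Not in the documents: visit-specific slopes and baseline SD. The pain entry threshold, which limits the baseline spread, is redacted. Assumed: baseline SD 1.5-3, follow-up SD 3-4, and a baseline-to-visit correlation changing linearly in log week. The table uses baseline SD 2, follow-up SD 3.5 and between-visit correlation 0.75 × 0.95^k, where k is the absolute log₂ ratio of the two week numbers.

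**Formulas** (large sample, complete data).

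- Slope of change on baseline at visit j: b_j = r_j × SD_follow-up/SD_baseline − 1.
- Common slope: c = 1′S⁻¹b / 1′S⁻¹1, where S is the residual covariance with visit-specific slopes.
- Week 12 residual variance with visit-specific slopes: v = SD_follow-up² × (1 − r₁₂²).
- Excess under the common slope: SD_baseline² × (b₁₂ − c)². Ratio = 1 + excess/v.
- If the planned model has 80% power, power with the term added = Φ(2.802 × √ratio − 1.960).

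| Correlation, Week 1 → Week 12 | b, Week 1 → Week 12 | c | v | Excess | Ratio | Power with term |
|---|---|---|---|---|---|---|
| 0.50 → 0.50 | −0.125 → −0.125 | −0.125 | 9.19 | 0 | 1.000 | 80.0% |
| 0.50 → 0.40 | −0.125 → −0.300 | −0.204 | 10.29 | 0.037 | 1.004 | 80.1% |
| 0.55 → 0.35 | −0.038 → −0.388 | −0.168 | 10.75 | 0.193 | 1.018 | 80.7% |
| 0.60 → 0.30 | 0.050 → −0.475 | −0.097 | 11.15 | 0.573 | 1.051 | 81.9% |
| 0.60 → 0.20 (extreme) | 0.050 → −0.650 | −0.087 | 11.76 | 1.268 | 1.108 | 83.9% |

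Fourth row in full: b₁₂ = 0.30 × 3.5/2 − 1 = −0.475, and v = 12.25 × 0.91 = 11.15. Excess = 4 × (−0.475 + 0.097)² ≈ 0.573, so the ratio is 1 + 0.573/11.15 = 1.051. Power = Φ(2.802 × 1.0253 − 1.960) = Φ(0.913) = 81.9%. The SD of change implied at Week 12 is √(12.25 + 4 − 2 × 0.30 × 7) = 3.47, below the SAP's 4.

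**Range over the assumed SDs.** Correlation 0.50 → 0.40 gives 1.000-1.004, 0.55 → 0.35 gives 1.003-1.018, and 0.60 → 0.30 gives 1.015-1.051. The two extreme patterns, 0.60 → 0.20 and 0.70 → 0.30, give 1.04-1.14, with power up to 84.8%. A constant correlation of 0.50 with follow-up SD rising from 3 to 4 also makes slopes differ, and gives at most 1.012.

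**Setting slopes directly** (baseline SD 1.5-2.5). Small drift gives about 1.001-1.002, −0.3 to −0.6 gives 1.005-1.017, and −0.2 to −0.7 gives 1.014-1.047.

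**Check with dropout.** For each scenario, 150 trials of 352 subjects were simulated with the table's SDs, a true Week 12 difference of −1 point and about 18% missing-at-random dropout. Both models were fitted by maximum likelihood.

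| Correlation | Estimate, common slope | Estimate, by-visit slope | SE² ratio |
|---|---|---|---|
| 0.50 → 0.50 | −1.009 | −1.008 | 1.000 |
| 0.55 → 0.35 | −1.046 | −1.039 | 1.022 |
| 0.60 → 0.20 | −1.067 | −1.064 | 1.122 |

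The SE² ratios agree closely with the closed form. The two models' estimates differ by at most 0.007 point. In the last row both depart from −1 by less than two Monte Carlo standard errors (0.464/√150 = 0.038).

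**The case against.** The strongest reply is that nothing here is wrong. The protocol, SAP text and code agree, a common baseline slope is a legitimate prespecified choice, and randomisation keeps the Week 12 contrast essentially unbiased. The documents give no slope, visit correlation or baseline SD, so a falling correlation is an expectation and not a documented fact. All of this stands. It makes the point an optional improvement and requires the wording to be conditional.

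Three stronger readings are tempting but unsupported.

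- A reader might infer that precision is certainly lost, or that the loss has a floor of one or two per cent. It has none: equal slopes cost nothing, and small drift costs a few tenths of a per cent.
- A reader might infer that a misspecified mean for subjects missing Week 12 weakens the missing-at-random adjustment. In the dropout simulation the two models gave practically the same estimate, so no material harm is shown. With 150 trials per scenario, very small biases cannot be ruled out.
- A reader might carry the percentages over to function (0-68) and stiffness (0-8). The model form is shared, but no inputs were tried for those scales.

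The reply that the unstructured covariance takes care of the misfit does not stand as far as precision goes, because the misfit ends up in the Week 12 variance.

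**Conclusion.** The point holds as a minor, conditional efficiency gain. The plan imposes one baseline slope on five visits, and no planned analysis relaxes it. If slopes differ by visit, Week 12 residual variance is inflated by about 0-5% under mild to moderate assumed drift. That is worth roughly 0 to 2 percentage points of power around 80%. Only extreme drift gives more, up to about 14%. These sizes depend on the assumed SDs, correlations and complete-data formula, which the documents neither confirm nor contradict beyond the bound of 4 on the endpoint SD. The validity of the primary comparison and its missing-data handling is not in question. Priority: nice to have.

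**What to change.** Before unblinding, add the baseline-by-visit interaction to the MMRM in SAP 16.1.3 and 16.2.2 and to the MODEL statement in Appendix 2. Five slopes replace one, so this adds four parameters per model. Analyses defined by reference to the primary MMRM, including Appendix 3, then inherit the term.

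The protocol specifies the same model, so changing the SAP alone would create a discrepancy. Either amend protocol 13.4.3.1, 13.4.3.2 and the synopsis, or record and justify the departure in SAP 3.3, which currently marks changes from the protocol as not applicable.

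The cost is four degrees of freedom and a documentation update. No new data are needed. If the slopes prove equal, almost nothing is lost: the simulated SE² ratio in that case was 1.000.

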16.1.4 COMPOSITE STRATEGY ANALYSIS FOR PRIMARY EFFICACY

Composite strategy will be applied to the stratum of subjects experiencing intercurrent events.

For the intercurrent events of study treatment discontinuation due to reasons related to study treatment (AE, LOE, etc.), the obtained WOMAC pain score will be addressed in the analysis by expecting the long-term benefit from the treatment for that subject to be zero from the time of intercurrent event. For the other intercurrent events, rescue medication use within 24 hours of WOMAC assessment, removal/detachment of study patch for more than 24 hours before WOMAC assessment, the obtained WOMAC pain score will not be included in the analysis.

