## 9.11. Rescue Medication

If needed, subjects will be allowed to take up to a maximum of 2 g (4 × 500 mg tablets) of oral APAP per day (as provided by the Sponsor or designee) as rescue medication for the treatment of the target knee pain of OA because of lack of efficacy of study drug (not for the non-target knee) if the subject does not feel enough pain relief by the study drug and any other aches they might experience during the trial such as headache and reduction of fever except within 3 calendar days prior to the Baseline Visit, on the day of Baseline Visit (V3), from Baseline Visit until Visit 4, within 2 calendar days prior to all subsequent visits (V5, V6, V7, and V8), and on the day of the clinic visits (V4, V5, V6, V7, and V8). Information regarding the use of rescue medication, such as the number of tablets taken, the time when it was taken, and the reason of use, will be recorded on the eDiary. Subjects should not use OTC APAP as rescue medication, i.e., they should only use the APAP provided by the Sponsor or designee. Rescue medication will be labeled appropriately for the study to ensure visual difference from similar OTC medications and to ensure proper understanding the rescue medication should be used for this study. NSAIDs or any other analgesics except study drug and rescue medication provided will not be permitted from the time that informed consent form is signed until study completion or early termination. Stable low doses of ASA up to 81 mg/day will be allowed.

Subjects are **NOT** allowed to apply study treatment drug (HP-5000/Placebo) on the non-target knee at any time during the Double-blind Treatment Phase.

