2.4 ESTIMANDS

The estimand for the primary efficacy analysis is the difference between the ITT population treatment groups (HP-5000 vs. placebo) in change from baseline WOMAC pain scores at Week 12 taking into account intercurrent events using the composite strategy specified in the [section 16.1.5](#).

Discontinuation of study treatment due to reasons related to study treatment (e.g. AEs, lack of efficacy (LOE), etc.), rescue medication use within 24 hours of WOMAC pain assessment, and removal/detachment of the patch for more than 24 hours before WOMAC pain assessment are defined as intercurrent events.

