5.1 INTENT-TO-TREAT SET[ITT]

Intent-to-treat (ITT) analysis set includes all consented and randomized subjects. Regardless of any protocol deviations and/or treatment compliance, analyses performed on the ITT set will be based on the randomized treatment assignment and all available data. The ITT set will be used as the primary set for analysis of primary and secondary efficacy endpoints. If a subject is randomized incorrectly or is administered the incorrect study drug, analyses of the ITT set will be based on the assigned treatment whereas all analyses of the safety analysis set will be based on the actual treatment.

Noven Pharmaceuticals, Inc.

Protocol HP-5000-US-07

Statistical Analysis Plan

Page 17 of 58

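### The primary estimand is labelled composite for all three intercurrent events, but scores affected by rescue or patch removal are excluded and treated as missing at random, which is a hypothetical strategy

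*SAP*

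**What the plan says.** SAP 2.4 defines the primary estimand as the HP-5000 versus placebo difference in change in WOMAC pain at Week 12 in the ITT population, "taking into account intercurrent events using the composite strategy". Besides treatment-related discontinuation, the listed events are "rescue medication use within 24 hours of WOMAC pain assessment, and removal/detachment of the patch for more than 24 hours before WOMAC pain assessment". SAP 16.1.3 repeats this.

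SAP 16.1.4 opens with "Composite strategy will be applied to the stratum of subjects experiencing intercurrent events" and then gives two different rules:

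- Treatment-related discontinuation is addressed by "expecting the long-term benefit from the treatment for that subject to be zero from the time of intercurrent event". No value or algorithm is given.
- For rescue and patch removal, "the obtained WOMAC pain score will not be included in the analysis".

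The synopsis and section 13.4.3.1 of the current protocol carry the same label and the same two rules. SAP 16.1.2 runs the primary MMRM on the assumption that "missing observations of change from baseline WOMAC pain score are missing at random". SAP 5.1 says that "analyses performed on the ITT set will be based on the randomized treatment assignment and all available data"; protocol 13.3 agrees.

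Protocol 9.11 permits "rescue medication for the treatment of the target knee pain of OA because of lack of efficacy of study drug", and also for headache, fever and other aches. It prohibits rescue from baseline to Visit 4, within 2 calendar days before Visits 5 to 8, and on visit days.

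**The concern.** A composite strategy makes the event part of the outcome: a subject who has the event is given a value that reflects it. For rescue and patch removal the plan does something else. It removes the score that was obtained, and the likelihood-based model in effect predicts it from the subject's other visits and from subjects in the same arm without the event. That asks what pain would have been had rescue not been taken, or had the patch stayed on.

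The estimand is what the primary p-value will be said to answer. One label covers two different questions, and the ITT sentence promises data that the analysis then sets aside. SAP 16.2.2 extends 16.1.3 to 16.1.6 to physical function and stiffness, so all three tests in the fixed sequence are affected.

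**Working it through.** **Step 1: label against handling.**

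| Event | Label in SAP 2.4 and 16.1.4 | What is done | Strategy this amounts to |
|---|---|---|---|
| Treatment-related discontinuation | Composite | Benefit taken as zero from the event | Composite-like |
| Rescue within 24 h | Composite | Score excluded, gap treated as MAR | Hypothetical |
| Patch off more than 24 h | Composite | Score excluded, gap treated as MAR | Hypothetical |

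**Step 2: does any planned analysis deliver a composite estimand for rescue?**

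- SAP 16.1.6 makes no adjustment for intercurrent events, so it keeps the obtained scores.
- Table B in SAP 16.1.5 names pattern-mixture and copy-reference methods for rescue and patch removal. The MNAR patterns beneath it are lack of efficacy, lack of efficacy plus AE, and all dropout. These are dropout reasons only, and the pattern-mixture text concerns data missing through early discontinuation.
- Even if the Appendix 3 shifts were applied to the excluded scores, they would worsen an MAR-imputed value. They would not assign a failure value.

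So none does.

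**Step 3: how far apart could the two estimands be?** The plan has no figure to reproduce here: effect size and sample size are redacted and event rates are not stated. Every input below is an assumption. Take placebo change −3.0 and SD 3.5 (SAP Appendix 3 implies only that it is below 4). Take effect size 0.25, so the difference is −0.25 × 3.5 = −0.875 and the HP-5000 change is −3.875. Let rP and rA be the proportions of Week 12 scores affected.

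- Exclusion under MAR, with events unrelated to pain: D = −3.875 − (−3.0) = −0.875 at any rates.
- Composite with zero change assigned: C = (1 − rA)(−3.875) − (1 − rP)(−3.0).
- Gap: C − D = 3.875 rA − 3.0 rP.

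| rP / rA | D | C |
|---|---|---|
| 2% / 2% | −0.875 | −0.857 |
| 5% / 5% | −0.875 | −0.831 |
| 10% / 10% | −0.875 | −0.788 |
| 10% / 5% | −0.875 | −0.981 |
| 5% / 10% | −0.875 | −0.638 |

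The two agree when rA/rP = 3.0/3.875, about 0.77. Below that ratio the composite shows a larger effect; above it, a smaller one.

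**Step 4: let rescue depend on pain.** A simulation of 2,000 trials kept the same means and SD, with 252 per arm (the size that gives 80% power at effect size 0.25, two-sided 0.05). The correlation between Weeks 8 and 12 was 0.6. Rescue became likelier with worse Week 12 pain and lowered the obtained score by 1.5. With about 11.5% placebo and 9.0% active events, the mean differences were:

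- scores excluded, MAR: −0.81
- obtained scores kept: −0.83
- zero change assigned: −0.79
- true value without rescue: −0.86

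The first three lie close together. Exclusion nevertheless gave a placebo mean of −3.29 against a true −3.01. It fell short of the no-rescue difference by about 0.05, so MAR does not fully recover even the hypothetical effect when rescue follows current pain.

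**The case against.** The strongest reply is that this is a naming defect. The exclusion is written out in SAP 16.1.4 and in the protocol, it can be programmed, and it may be a legitimate choice. That stands. A reader might infer that the study report would say rescue counted against the subject; the documents do not support this, because they disclose the exclusion each time.

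Three other stronger readings also fail:

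- *The whole primary analysis is hypothetical.* Discontinuation has a composite-like rule, so the estimand is a mixture.
- *All the excluded scores are treatment failures.* The event is any rescue within 24 hours, whatever the reason, including headache and fever. Protocol 9.2 recognises accidental detachment. Only rescue for target-knee pain can be read as lack of efficacy.
- *ITT subjects are removed.* Only scores at affected visits are dropped, and a specific rule can qualify a general one. The exception does need to be stated.

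It can also be said that stress tests are already planned. Table B shows that intent, and Appendix 3 speaks of shifting all imputed data. But Appendix 3 reports by dropout reason and justifies its shifts for discontinued subjects, so the excluded scores are not clearly reached.

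Finally, a WOMAC score within 24 hours after rescue should be uncommon, because that use would breach the prohibition before and on visit days. This limits the size of the problem, not its existence.

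**Conclusion.** The point holds as a mismatch between the named strategy and the specified handling for two of the three intercurrent events, together with an unstated exception to the ITT sentence. It changes what the primary and key secondary tests can be said to show.

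The numerical effect is unknown. Under the assumptions in Step 3 the composite difference runs from about 27% smaller (0.638/0.875 = 0.73) to 12% larger (0.981/0.875 = 1.12) than the excluded-score difference. Those extremes need event rates of 5% to 10% that differ twofold between arms. At 2% in each arm the gap is 0.018, and in the pain-dependent simulation it was about 0.01 to 0.02. A reader might take the wider range as an estimate of bias; it is not one, because the documents give no event rates. Patch removal was not quantified separately.

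**What to change.** 1. In the protocol synopsis and 13.4.3.1, and in SAP 2.4, 16.1.3 and 16.1.4, name the strategy for each event: composite for treatment-related discontinuation; hypothetical, estimated under MAR, for rescue within 24 hours and patch off for more than 24 hours.
2. Add that exception to the ITT sentence in SAP 5.1 and protocol 13.3.
3. In SAP 16.1.5, extend the MNAR patterns to the excluded rescue and patch-removal scores so that they match Table B, and align Appendix 3.
4. Add one supplementary MMRM in which WOMAC scores obtained within 24 hours after rescue for target-knee pain are set to change from baseline = 0, and show it next to 16.1.6. Protocol 9.11 has the time and reason of each use recorded in the eDiary, so these scores can be identified. State the value explicitly, since 16.1.4 gives none for zero benefit.

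Two cross-references can be corrected in the same edit: SAP 2.4 points to 16.1.5 for the composite strategy, which is in 16.1.4, and SAP 16.1.2 points to 16.1.4 for the sensitivity analyses, which are in 16.1.5.

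The cost is wording in both documents, a wider set of MNAR patterns and one extra model, all settled before unblinding. The primary computation is unchanged. The downside is a more narrowly stated primary claim.
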